1 ABBREVIATIONS

AE	Adverse Event
ALT	Alanine aminotransferase
AST	Aspartate aminotransferase
CCL2	Chemokine (C-C motif) ligand 2
CXCL13	Chemokine (C-X-C motif) ligand 13
CXCR3	Chemokine (C-X-C motif) receptor 3
ELISA	Enzyme-linked Immunosorbent Assay
EDSS	Expanded Disability Status Scale
GCP	Good Clinical Practice
ICH	International Conference on Harmonisation of Technical Requirements for Registration of Pharmaceuticals for Human Use
MS	Multiple Sclerosis
PASAT	Paced Auditory Serial Addition Test
RRMS	Relapsing-remitting Multiple Sclerosis
SAE	Serious Adverse Event
SDMT	Symbol Digit Modalities Test
TNF	Tumor Necrosis Factor
VLA	Very Late Antigen
WBC	White Blood Cell

2 BACKGROUND

The purpose of this statistical plan is to define the tables, lists, data summaries and graphs to be prepared and to determine the statistical methods to be used for the analysis of the results of the study titled, “Effects of Fingolimod (Gilenya®) on Cytokine and Chemokine Levels in Relapsing Remitting Multiple Sclerosis Patients”.

This statistical analysis plan has been prepared in pursuant to and in line with ICH-GCP principles and protocol no. CFTY720DTR04.

3 OBJECTIVES OF THE STUDY

3.1. PRIMARY OBJECTIVE

The primary objective of this study is to evaluate the differences between serum cytokine and chemokine levels of healthy controls and multiple sclerosis patients.

3.2. SECONDARY OBJECTIVE

The secondary objective of this study is to test the predictive value of cytokine/chemokine changes measured in the 3rd and 6th months on the PASAT, SDMT, 9-Hole peg test, timed 25-foot walk, EDSS and relapse rate observed after 6 months of treatment.

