**Table 6-1 Assessment schedule for MS Patients**

Visit	1	2	3
Day	0	90±7	180±14
Obtain Informed Consent	X		
Evaluation of Inclusion/Exclusion Criteria	X		
Demographic and Previous Data	X		
Other Concomitant Diseases	X		
MS and Treatment History	X		
Assessment of the MS Relapses Within Last 2 Years	X		
Recording of Relapses			X
Pregnancy Test (Urine)	X		
Varicella-Zoster Ab	X		
Hematology *	X**	X	X
Clinical Chemistry *	X**	X	X
ECG	X		
Optical Cohorence Tomography	X	X	
EDSS Measurements	X		X
PASAT Measurements	X		X
Symbol Digit Modalities Test (SDMT) Measurements	X		X
9-Hole Peg Test	X		X
25 Foot Walk Test	X		X
Collecting Serum and Blood Samples for Biomarker Research	X	X	X
Dispense Study Medication	X	X	
First Dose Administration	X		
End of the Study Visit			X

\* Hematology: Leukocytes, Hemoglobin, Absolute Neutrophilis, Absolut, Lymphocyte, Platelet  
 Clinical Chemistry: AST, ALT, BUN, Creatinine, Total Cholesterol, Tryglicerides, LDL-K, HDL-K, TSH,ST4, Glucose, HbA1c

\*\* If the patient has hematology and clinical chemistry results within the last 1month, the tests do not have to be repeated.

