### **6.6      Other assessments**

For clinical measures; EDSS and relapses will be recorded after 6 months of treatment. EDSS scoring will also be performed at study entry. PASAT, 9-Hole Peg test, timed 25-foot walk and SDMT tests will be performed only at study entry and termination after 6 months.

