## **9.5 Statistical model, hypothesis, and method of analysis**

There is no special hypothesis planned for this study.

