6.2 CLINICAL DATA

- **Previous MS treatment** of the patients will be expressed as n and %.
- **Age of onset of MS** of the patients will be tabulated by calculating n, mean, standard deviation, minimum, maximum and median.
- **Duration of MS (years)** of the patients will be tabulated by calculating n, mean, standard deviation, minimum, maximum and median.
- **MS relapses in the previous 2 years** of the patients will be tabulated by calculating n, mean, standard deviation, minimum, maximum and median.
- **MS relapses requiring corticosteroids in the previous 2 years** of the patients will be tabulated by calculating n, mean, standard deviation, minimum, maximum and median.
- **MS relapses in the previous 1 year** of the patients will be tabulated by calculating n, mean, standard deviation, minimum, maximum and median.
- **MS relapses requiring corticosteroids in the previous 1 year** of the patients will be tabulated by calculating n, mean, standard deviation, minimum, maximum and median.
- **Duration of treatments (months)** of the patients will be tabulated by calculating n, mean, standard deviation, minimum, maximum and median.
- **Relapse rates** of the patients will be evaluated.

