6.4 ASSESSMENTS OF SCALE

Patients' **EDSS, PASAT, SDMT, 9-hole peg test** and **timed 25-foot walk test** values will be tabulated by calculating mean and standart deviation and compared as Visit 1 vs. Visit 3 by using appropriate statistical test. Wilcoxon test will be used in the dependent variables with non-normal distributions whereas Paired sample t test will be used in the dependent variables with normal distributions.

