6.5 ASSESSMENT OF CYTOKINE AND CHEMOKINE LEVELS

6.5.1 ELISA

Subjects' **IL-4, IL-6, IL-8, IL-9, IL-10, IL-13, IL-17, IL-23, IFN- γ , TNF- α , VLA4, CCL2, CCL5, CXCR3 and CXCL13** values will be tabulated by calculating mean and standart error and compared as Control group vs. Visit 1 (MS patients), Visit 1 (MS patients) vs. Visit 2 (MS patients), Visit 1 (MS patients) vs. Visit 3 (MS patients) and Control group vs. Visit 3 (MS patients) by using appropriate statistical test. Mann Whitney U test with significance level of 0.05 was used for the independent variables since non-normal distributions had been observed. Wilcoxon test was used for the dependent variables with non-normal distributions. For the independent variables with normal distributions Independent Sample t test was used whereas Paired sample t test was used for the dependent variables with normal distributions.

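### The plan contains no analysis linking a cytokine change to a clinical outcome, so its secondary objective gets no result; the month-6 change could show only concurrent association.

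*SAP*

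**What the plan says.** SAP 3.2 sets one secondary objective: to "test the predictive value of cytokine/chemokine changes measured in the 3rd and 6th months on the PASAT, SDMT, 9-Hole peg test", followed by the timed 25-foot walk, EDSS and relapse rate after 6 months of treatment. Protocol 2.2 and the synopsis say the same.

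The analyses that touch these variables are:

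- **Scales (SAP 6.4).** The five scales' "values will be tabulated by calculating mean and standart deviation and compared as Visit 1 vs. Visit 3", using a paired t or Wilcoxon test.
- **Relapse (SAP 6.2).** Relapse rates "of the patients will be evaluated". No method or predictor is named.
- **Markers (SAP 6.5.1 and 6.5.2).** The 15 ELISA and 8 flow cytometry markers are "compared as Control group vs. Visit 1 (MS patients), Visit 1 (MS patients) vs. Visit 2 (MS patients", then Visit 1 vs Visit 3 and controls vs Visit 3.
- **Protocol 9.** Section 9.4 lists variables without a method. Section 9.5 states "There is no special hypothesis planned for this study". Section 9.6, on supportive analyses, is marked not applicable.

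On timing, the row "Collecting Serum and Blood Samples for Biomarker Research" in Protocol Table 6-1 is marked at Visits 1, 2 and 3. The scales are marked at Visits 1 and 3 only, and on-study relapses at Visit 3. Protocol 6.6 adds that "EDSS and relapses will be recorded after 6 months of treatment". SAP 5 ends patient follow-up at 6 months.

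**The concern.** Whether a marker change predicts an outcome is a question about patients one by one: did those whose marker moved more do better or worse? A mean shift in a marker and a mean shift in a scale, tested separately, cannot answer it. The planned tables could be complete and correct and still say nothing about the secondary objective.

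Two consequences follow. If the objective is to be reported at all, someone must choose a model, a marker set and a way of handling many tests outside the plan, possibly with marker and outcome data in hand. And because the objective treats months 3 and 6 alike, a month-6 association measured at the same visit as the outcome could be reported as prediction.

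**Working it through.** **1. The plan's own figure.** The one sample-size calculation (SAP 5.1, Protocol 9.8) takes SD 15 and difference 7 pg/ml for IL-17, 90% power and alpha 0.05. Treating 15 as the SD of paired differences, n = (15 × (1.960 + 1.282) / 7)² = 48.2, so 49 pairs; exact t power at 50 pairs is 0.899. The stated 50 pairs reproduce. They concern a mean difference in one marker. No power is given for any marker-outcome association.

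**2. Search for a linking analysis.**

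| Section | Marker? | Clinical outcome? | Both in one analysis? |
|---|---|---|---|
| SAP 6.1 demographics | no | no | no |
| SAP 6.2 history, relapse rates | no | yes | no |
| SAP 6.3 laboratory tests | no | no | no |
| SAP 6.4 scales | no | yes | no |
| SAP 6.5 ELISA, flow cytometry | yes | no | no |
| SAP 6.6 safety | no | no | no |
| Protocol 9.4 | listed | listed | no method given |

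The count of linking analyses is zero. The SAP section numbering is continuous and SAP 6 shows no redaction.

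**3. Timing.**

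- Month-6 change against the scales: both at Visit 3, so the nominal gap is 0 days. Relapses counted up to Visit 3 nominally precede that sample. Protocol 5.4.6 delays sampling after corticosteroids, so a delayed sample could even follow the scales.
- Month-3 change against the scales, Table 6-1 (days 90±7 and 180±14): 180 − 90 = 90 days; in window, 166 − 97 = 69 to 194 − 83 = 111.
- The same on the synopsis and Protocol 1.2 schedule (12±1 and 24±2 weeks, that is days 84±7 and 168±14): 168 − 84 = 84 days; in window, 154 − 91 = 63 to 182 − 77 = 105.
- Both ranges come before any steroid delay or the flexible visit wording under Table 6-2.

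**4. Size of the missing analysis (month-3 change, five scales).** Serum only: 15 × 5 = 75 tests, with 75 × 0.05 = 3.75 false positives expected if nothing is predictive. With flow markers: (15 + 8) × 5 = 115 tests, with 5.75 expected.

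**5. Detectable association.** Smallest partial correlation with 80% power, two-sided, two covariates: r = tanh[(z(1−α/2) + 0.842) / √(n − 5)]. At n = 60 and α = 0.05: (1.960 + 0.842) / √55 = 0.378, and tanh gives 0.361.

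| α | n = 48 | n = 60 | n = 80 |
|---|---|---|---|
| 0.05 (one test) | 0.403 | 0.361 | 0.313 |
| 0.05/75 | 0.570 | 0.517 | 0.454 |
| 0.05/115 | 0.582 | 0.528 | 0.465 |

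Three values of n are shown because SAP 5 gives 80 patients, SAP 5.1 gives 60 eligible with 20% drop-out (60 × 0.8 = 48), and Protocol 5.4.9 replaces withdrawn patients. The last two rows are Bonferroni levels, hence conservative bounds if the false-discovery rate is controlled. The formula is for a linear model and does not carry over to an ordinal EDSS model.

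**6. Relapses after Visit 2.** The documents give no rate. Assuming 0.2 to 0.5 per patient-year over 0.25 year: 60 × 0.2 × 0.25 = 3.0 to 60 × 0.5 × 0.25 = 7.5 events; with 80 patients, 4 to 10.

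**The case against.** The best defence is that the study is openly exploratory: the protocol plans no special hypothesis, the primary objective does not depend on this, and all patients receive the same drug, so the open label reveals no allocation. That supports a short exploratory section instead of formal error control. It does not excuse a stated objective with no analysis, since the SAP says its purpose is to determine the statistical methods.

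A second defence reads the outcomes as observed later than month 6. Follow-up stops at 6 months, and the 30-day contact under Table 6-2 is for safety, so this fails.

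Three stronger readings are tempting, and the documents do not support them.

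- **That the month-3 half also fails as prediction, because a relapse or steroid course before Visit 2 may affect both marker and score.** That is a possible common cause, not concurrency. A marker can predict without being causal, and Protocol 5.4.6 already separates sampling from steroid treatment by at least a month. It bears on interpretation only.
- **That the model is already being chosen after seeing results.** The SAP's past tense, "since non-normal distributions had been observed", concerns test choice for group and visit contrasts. It suggests that marker data had been seen, but not that markers had been set against outcomes. Protocol 6.5.1 has the marker analysis done cumulatively at the end.
- **That relapse timing cannot be recovered.** The relapse definition in Protocol 6.4 relies on onset, so onset must be established. Whether the date is captured in the CRF is not shown.

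**Conclusion.** The concern holds on two counts. No planned analysis joins a marker change to an outcome, so the secondary objective has no planned result. And the month-6 change, at a nominal gap of 0 days, can support concurrent association only. Both follow from reading the sections and visit schedule together and depend on no assumed figure.

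The scope is limited. The primary comparison with healthy controls is untouched, and the data already scheduled allow a prospective month-3 analysis. That analysis would be sensitive only to moderate or strong associations: about 0.40, 0.36 or 0.31 at n = 48, 60 or 80 for one test, and at most about 0.58, 0.53 or 0.46 under Bonferroni over 115 tests. These values assume a linear model with two covariates. The relapse result would be very imprecise; its event counts rest on an assumed annual rate. I describe this as the only secondary objective shown because one line after Protocol 2.2 in the contents is redacted; the SAP lists a single one. The plan should be changed, but the trial's main result is not at risk.

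**What to change.** 1. **Add an SAP section for the month-3 change.** For each of the five scales, regress the Visit 3 score on the Visit 1-to-Visit 2 analyte change, adjusting for the Visit 1 score and Visit 1 analyte level. Use rank-based or transformed analyte values where distributions are non-normal, and a rank or ordinal model for EDSS. State whether flow markers are included. Either control the false-discovery rate across all 75 or 115 tests, or label the results exploratory.
2. **Relabel month 6.** Report the Visit 1-to-Visit 3 change as concurrent association, and reword SAP 3.2 and the matching protocol text (synopsis, 1.2 and 2.2). Reconcile the day-based and week-based schedules so that the interval is unambiguous.
3. **Relapse.** Count only onsets after the actual Visit 2 sample date, if onset dates are captured, and report descriptively.
4. **Status.** If marker-outcome data have already been examined, label the section post hoc.
5. **Optional.** Add a sensitivity analysis for relapse or steroid use before the Visit 2 sample, presented as a possible common cause and not as a timing problem. Steroid use is already recorded in the CRF.

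The cost is an SAP revision and a wording amendment under Protocol 11.1 (sponsor, IRB/IEC and, where required, health authorities). The drawback is limited power, which the new section should state.

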4 STUDY DESIGN

This study is a multi center, open label study.

[figure not shown]
80 relapsing remitting MS (RRMS) patients will be recruited according to the Mc Donald's criteria and 60 healthy controls will be recruited as the control group. All subjects will sign an informed consent that will be approved by the local Ethics Committee and the applicable health authorities prior to venipuncture. Basal EDSS, relapses during the last 2 years, paced auditory serial addition task (PASAT), 9-Hole peg test, timed 25-foot walk and single digit modalities test (SDMT) scores will be recorded before study entry. Serum and blood samples will be collected from each participant after evaluation for inclusion and exclusion criteria. Additional serum and blood samples at 2 different time points will be collected from MS patients at months 3 (± 1 week) and 6 (± 2 weeks) after starting fingolimod 0.5 mg/day po. treatment (Figure 1). Serum samples will be stored at -20°C at local centers for a longest duration of two weeks and kept frozen at -80°C [REDACTED]

Whole blood samples will be dispatched

In order to perform flow cytometry assay for intracellular cytokine measurement PBMC will be isolated freshly.

EDSS and relapses will be recorded after 6 months of treatment. PASAT, 9-hole peg test, timed 25-foot walk and SDMT's will be performed only at study entry and termination after 6 months (Figure 1).

Figure 1: Study protocol (PASAT: Paced auditory serial addition task, SDMT: single digit modalities test, FACS: Flow assisted cell sorting, flow cytometry)

5 ANALYZED POPULATIONS

The study will include only 80 relapsing remitting MS patients and 60 healthy controls without any known autoimmune disease. RRMS patients will be followed for 6 months.

5.1. SAMPLE SIZE CALCULATION

Due to the lack of previous studies using all of the cytokines and chemokines and multitudinous analyses, it is difficult to estimate a precise sample size for our study. Despite this, our previous publications indicate that the basal IL-17 concentration is normally distributed with a mean of 32 pg/ml (\pm stdev of 15 pg/ml) in RRMS patients. If the true difference in the mean concentration of matched pairs is 7 pg/ml, we will need to study 50 pairs of subjects to be able to reject the null hypothesis with a power of 90%. The Type I error probability associated with this test of this null hypothesis is 0,05.

With assumption of drop out rate of 20% minimum 60 RRMS patients and 60 healthy control subjects should enroll to the study. Due to expected high rate of screen failure patients, we decided to screen 80 RRMS patients in order to reach 60 eligible RRMS subjects for the study.

6 ANALYSIS PLAN

Data analysis will be performed after all of the data is collected from the enrolled patients. All MS patients and control group will be accepted as the analysis sets.

Cytokine and chemokine levels will be analyzed cumulatively at the end of the study. The results will be recorded to the blood sampling logs and laboratory logs cumulatively.

6.1 DEMOGRAPHICS

- **Gender:** Subjects, male and female, in both groups (Control & MS patients) will be expressed separately as n and %.
- **Age:** Age data for subjects in the “Control” and in the “MS patients” groups will be tabulated by calculating n, mean, standard deviation, minimum, maximum and median.

6.2 CLINICAL DATA

- **Previous MS treatment** of the patients will be expressed as n and %.
- **Age of onset of MS** of the patients will be tabulated by calculating n, mean, standard deviation, minimum, maximum and median.
- **Duration of MS (years)** of the patients will be tabulated by calculating n, mean, standard deviation, minimum, maximum and median.
- **MS relapses in the previous 2 years** of the patients will be tabulated by calculating n, mean, standard deviation, minimum, maximum and median.
- **MS relapses requiring corticosteroids in the previous 2 years** of the patients will be tabulated by calculating n, mean, standard deviation, minimum, maximum and median.
- **MS relapses in the previous 1 year** of the patients will be tabulated by calculating n, mean, standard deviation, minimum, maximum and median.
- **MS relapses requiring corticosteroids in the previous 1 year** of the patients will be tabulated by calculating n, mean, standard deviation, minimum, maximum and median.
- **Duration of treatments (months)** of the patients will be tabulated by calculating n, mean, standard deviation, minimum, maximum and median.
- **Relapse rates** of the patients will be evaluated.

6.3 LABORATORY TESTS

6.3.1 Clinical Biochemistry

Patients' **AST, ALT, BUN, Creatinine, Total Cholesterol, Tryglycerides, LDL-C, HDL-C, TSH, ST4, Glucose and HbA1c** values will be tabulated by calculating mean and standart deviation and compared as Visit 1 vs. Visit 2 and Visit 1 vs. Visit 3 by using appropriate statistical test. Wilcoxon test will be used in the dependent variables with non-normal distributions whereas Paired sample t test will be used in the dependent variables with normal distributions.

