#### **5.4.9 Discontinuation of study treatment and premature patient withdrawal**

Patients may voluntarily withdraw from the study for any reason at any time. They may be considered withdrawn if they state an intention to withdraw, fail to return for visits, or become lost to follow-up for any other reason.

If premature withdrawal occurs for any reason, the investigator must make every effort to determine the primary reason for a patient's premature withdrawal from the study and record this information on the Study Completion CRF.

The investigator should discontinue study treatment for a given patient or withdraw the patient from study if, on balance, he/she believes that continuation would be detrimental to the patient's well-being.

Study drug must be discontinued for a given patient if the investigator determines that continuing it would result in a significant risk for that patient. The following conditions/events may be considered sufficient to support a decision about the study drug discontinuation in individual cases:

- serious adverse event (e.g. cardiac failure, diagnosed malignancy)
- abnormal laboratory value(s) including liver function tests or abnormal test result(s) (e.g. PFTs, MRI and ophthalmic findings). See below and Appendix 7 and 8 for guidance for safety monitoring
- withdrawal of consent (e.g., in case the patient does not consent to continue in the study after a confirmed relapse or disability progression)
- pregnancy
- use of prohibited medications, listed in Section 5.1 and 6.6.5
- adverse events
- protocol violation
- unsatisfactory therapeutic effect
- patient's condition no longer requires study treatment
- administrative problems (e.g. patient's non-compliance)

In addition, the following conditions based on the Guidance on safety and ophthalmic monitoring should result in study drug discontinuation:

- Hepatic Increase in ALT > 5 x ULN Increase in AST > 5 x ULN
- New neurological symptoms accompanied by MRI findings unexpected for MS
- Diagnosis of macular edema

---

- Decrease in visual acuity with abnormal OCT (increase in central foveal thickness of > 20% compared to screening or cystic changes in the macula).

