Patients who discontinue study drug should not be considered withdrawn from the study, unless one of the conditions listed above have been met. The sponsor should be notified about any decision regarding discontinuation of the study medication. Patients who discontinue the study drug should be treated according to the best standard of care. In addition to scheduled visits, patients who discontinue study drug due to adverse events or abnormalities on safety monitoring tests must be followed up with additional visits as needed in order to confirm the resolution of abnormalities. A Study Drug Discontinuation CRF should be completed, giving the date and primary reason for stopping the study drug.

For patients who are lost to follow-up (i.e. those patients whose status is unclear because they fail to appear for study visits without stating an intention to withdraw), the investigator should show "due diligence" by documenting in the source documents steps taken to contact the patient, e.g. dates of telephone calls, registered letters, etc.

Patients who are prematurely withdrawn from the study will be replaced by an equal number of newly enrolled patients.

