6.3.2 Hematology

Patients' **WBC, Absolute Lymphocyte Count, Platelet, Absolute Neutrophil Count and Hemoglobin** values will be tabulated by calculating mean and standart deviation and compared as Visit 1 vs. Visit 2 and Visit 1 vs. Visit 3 by using appropriate statistical test. Wilcoxon test will be used in the dependent variables with non-normal distributions whereas Paired sample t test will be used in the dependent variables with normal distributions.

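### The planned ALT and AST summaries (mean, SD, paired tests) do not count patients who cross the protocol's own 5 x ULN discontinuation threshold

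*SAP*

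**What the plan says.** **Analysis.** SAP 6.3.1 covers twelve chemistry variables, including AST and ALT: "values will be tabulated by calculating mean and standart deviation and compared as Visit 1 vs. Visit 2 and Visit 1 vs. Visit 3". The test depends on the distribution: "Wilcoxon test will be used in the dependent variables with non-normal distributions whereas Paired sample t test will be used". The section plans no count against ULN, shift table, worst post-baseline value, listing, minimum, median or maximum. SAP 6.1 and 6.2 do give minimum, maximum and median for age, MS duration and relapse history.

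**Threshold.** Protocol 5.4.9 lists "Hepatic Increase in ALT > 5 x ULN Increase in AST > 5 x ULN" among conditions that "should result in study drug discontinuation". Patients who stop for adverse events or safety-test abnormalities "must be followed up with additional visits as needed in order to confirm the resolution of abnormalities". The stop is also documented: "A Study Drug Discontinuation CRF should be completed, giving the date and primary reason for stopping the study drug". No SAP table reports these reasons.

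**Other safety output.** SAP 6.6 tabulates AEs, SAEs, and patients who died or had other serious or clinically significant events. Protocol 9.7 summarises AEs, SAEs and pregnancies. The synopsis and Protocol 6.5 say that no safety analysis is planned; these passages should be reconciled.

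**Recording.** Protocol 6.5.2 and 6.5.3 direct clinically significant ECG and OCT abnormalities to the Medical History/Adverse event CRF page. Protocol 6.5.1.1 and 6.5.1.2, on haematology and chemistry, contain no such instruction.

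**The concern.** The protocol's liver criterion is a yes/no fact about one patient. The SAP's laboratory analysis asks a different question: whether the centre of the distribution moved between visits. In a group of about 60, a few very high values shift the mean little and hardly affect a signed-rank test.

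Followed as written, the laboratory section of the report could say that ALT and AST did not change significantly while one or more patients had met the condition for stopping study drug. A reader of that section could not tell how many had.

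**Working it through.** There is no stated figure to reproduce. The check has two parts: where a case could appear, and how the planned test responds to a few cases.

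**1. Where a patient above 5 x ULN could appear**

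- SAP 6.3.1 mean and SD: the value contributes, but the patient is not counted and the threshold is not applied. A raised SD hints at an outlier without saying how many patients or how high.
- SAP 6.3.1 paired test: the value contributes one signed rank or one difference.
- SAP 6.6: the patient appears if the site reports an AE or SAE, or if someone judges the event clinically significant. No laboratory rule makes that automatic.
- Study Drug Discontinuation CRF: date and reason are collected, but the SAP has no table for them.

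**2. Response of the planned test**

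Inputs:
- n = 60 patients, the eligible number in SAP 5.1.
- Assumed, because the documents give no ALT distribution: usual level 0.6 x ULN; SD of within-patient change 0.15 to 0.25 x ULN; no general drug effect.
- k = 1, 2 or 3 patients (1.7%, 3.3%, 5.0%) at 6 x ULN, a change of 6.0 - 0.6 = 5.4 x ULN.

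Shift in the mean = k x 5.4 / 60:
- k = 1: 0.09, so the visit mean goes from 0.60 to 0.69 x ULN
- k = 2: 0.18, mean 0.78 x ULN
- k = 3: 0.27, mean 0.87 x ULN

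The visit mean stays below 1 x ULN in all three.

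Which test applies: in simulation with k of 1 to 3, Shapiro-Wilk rejected normality of the changes in 100% of runs. If normality is judged on the changes, the SAP's rule leads to Wilcoxon.

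Wilcoxon by normal approximation. With no abnormal patient, the SD of the positive rank sum is sqrt(n(n+1)(2n+1)/24) = sqrt(60 x 61 x 121/24) = 135.8. The two-sided 5% limit is 1.96 x 135.8 = 266.2 from its centre. The k abnormal patients hold the top k ranks, always positive. This moves the centre by half the sum of those ranks, and only the other m = 60 - k ranks vary, with SD s = sqrt(m(m+1)(2m+1)/24).

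| k | shift | s | (266.2 - shift)/s | (-266.2 - shift)/s | rejection |
|---|---|---|---|---|---|
| 0 | 0 | 135.8 | 1.96 | -1.96 | 5.0% |
| 1 | 60/2 = 30 | 132.5 | 1.78 | -2.24 | 3.7% + 1.3% = 5.0% |
| 2 | (60+59)/2 = 59.5 | 129.2 | 1.60 | -2.52 | 5.5% + 0.6% = 6.1% |
| 3 | (60+59+58)/2 = 88.5 | 125.9 | 1.41 | -2.82 | 7.9% + 0.2% = 8.1% |

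Simulation agrees: about 5% to 9% for k of 1 to 3 across the assumed SDs. A variant with separate baseline variation and cases set at 5.5 x ULN gave 5.6%, 6.2% and 9.8%.

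The same formula gives 5.0%, 6.3% and 8.7% for n = 50, and 5.0%, 5.8% and 7.4% for n = 80. It uses only ranks, so it does not depend on the assumed ALT level or SD. It needs only that the abnormal changes are the largest and the other changes are symmetric about zero.

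**The case against.** **SAP 6.6 can show these cases.** A reader might infer that the plan cannot reveal them at all. The documents do not support that. A rise that meets a discontinuation condition fits the ordinary meaning of a clinically significant event, the sponsor must be told of the stop, and a CRF records the reason. What remains is narrower: display in SAP 6.6 depends on site reporting, with no laboratory definition and no ULN count.

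**The paired t test.** One might argue that an outlier inflates the SD and so makes the t test less likely to reject. That is true of the t test, but the SAP sends non-normal variables to Wilcoxon, and these changes would be clearly non-normal. The argument would matter only if normality were judged in some other way.

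**Values off schedule.** It is tempting to say that the abnormal values will lie outside the analysed visits. Table 6-1 schedules chemistry at Visits 1, 2 and 3, so routine detection falls at visits that the SAP analyses, and the additional visits serve to confirm resolution. An unscheduled peak is possible but is not shown to be usual.

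**Missing Visit 3.** Nor do the documents establish that a patient who stops drug has no Visit 3 value. Protocol 5.4.9 generally keeps such patients in the study with scheduled visits, while Protocol 6.3 treats one month off drug in total as withdrawal. Those passages must be reconciled, but that is a separate matter.

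**Safety is not an objective.** The objectives concern biomarkers and prediction. This stands and lowers the priority. It does not remove the point, because the SAP itself chose to run significance tests on ALT and AST.

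**Conclusion.** The point holds as a low-priority improvement. SAP 6.3.1 has no output that counts patients above the protocol's ALT/AST threshold, and its paired test is nearly blind to a few such patients: about 5% to 9% rejection with 1 to 3 of 60, against 5% with none. Cases may still reach the reader through SAP 6.6, but only by site reporting.

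The rejection figures assume no general shift in ALT. With a general shift the test could well be significant, but it still would not say how many patients crossed the threshold. No primary or secondary result, sample size or alpha is affected.

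The point does not extend to SAP 6.3.2. The haematology summary, "values will be tabulated by calculating mean and standart deviation", has the same form, but the protocol sets no numeric haematology threshold for it to miss. Nothing here bears on whether the 5 x ULN condition is the right one.

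**What to change.** In SAP 6.3.1:

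- Add the number and percentage of treated patients with any post-baseline ALT or AST above 5 x ULN, using scheduled and any unscheduled values, with a listing of those patients.
- Add minimum, median and maximum per visit for ALT and AST.
- Label the paired tests as descriptive.

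A count also makes a zero readable. With no case among 60, the exact one-sided 95% upper limit is 1 - 0.05^(1/60) = 4.9%; among 80 it is 1 - 0.05^(1/80) = 3.7%.

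The cost is one extra table with its listing. The database must hold the ULN and any unscheduled results, and the documents do not show that either is captured, so this should be confirmed before lock.
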